### **7.3.3. The investigator's responsibilities for submission of reports on serious adverse events**

#### **Completion of SAE report form:**

In case of development of SAE, the investigator or other authorized employee of the trial site has to complete the SAE report form with indication of information on this case. SAE report forms will be provided to investigators during the training on completion of SAE report form. The information stated in the SAE report has to correspond to the data provided in CRF sections "Adverse events", "Concomitant therapy", and "Results of laboratory investigations". SAE has to be included in source medical documents of a study subject.

#### **Report on SAEs:**

Strictly confidential. Proprietary Information.  
[name]

The investigators has to report in a prompt manner on all cases of SAE developing in study subjects from the moment of administration of the first dose of the study product until the Study end visit.

When reporting on the SAE, the investigator has to complete an SAE report form and send it to the sponsor's contact person by fax or send a scanned copy of the report by e-mail within 24 hours from recording of SAE.

**All serious adverse events have to be reported on in a prompt manner by sending a completed SAE report form to the sponsor's contact person by fax and/or e-mail:**

[name]

**[contact]**

[contact] (+114)

*e-mail:* [[contact]](mailto:[contact])

[name]

Before sending a report about an SAE, the study monitor should be notified by phone about the submission of the fax.

The SAE report has to be prepared irrespective of relationship, detected by the investigator or an authorized employee, between the observed SAE and administration of the study product.

After submitting an urgent SAE report, the investigator must, within 48 hours, submit a detailed report with detailed information on SAE to the study sponsor, which will allow the latter to make an assessment about the need to review the benefit-risk ratio of the clinical study.

If an SAE associated with administration of the study product is recorded in a study subject, it has to be reported even if the study has been completed.

All SAEs and their complications have to be monitored up to their resolution or stabilization of a study subject's condition.

#### **7.3.4. The sponsor's responsibilities for submission of SUADR reports and other safety reports**

##### **Reporting of SUADRs:**

**A serious unexpected adverse drug reaction (SUADR) is an SAE associated with the study product administration, i.e. a reaction the nature and severity of which does not correspond to the known information on the medicinal product.** The following documents shall be used for determination of predictability of the SAE: investigator's brochure, draft instruction for medical use, and the study protocol.

---

Strictly confidential. Proprietary Information.  
[name]

Pharmacovigilance officer of the sponsor company has to send express reports on SUADR to LECs of trial sites and to regulatory authorities. Pharmacovigilance officer of the sponsor company also has to inform the investigators on all SUADRs recorded during the study.

Reports on SUADRs causing death or posing a threat to life of a study subject has to be sent to LECs of trial sites and to regulatory authorities within 7 calendar days from the date of receipt of the investigator's SAE report. If full information on a death or development of a life-threatening condition is not available to the sponsor as of the date of the urgent report, the sponsor has to take all measures to obtain full information provided in the form of a subsequent urgent report on identified SUADRs within 8 calendar days from the date of submission of initial report.

Reports on all other SUADRs have to be submitted by the study sponsor to LECs of trial sites and to regulatory authorities within 15 calendar days from the date of receipt of the investigator's SAE report.

If new significant information on identified SUADR becomes available to the sponsor, this information has to be provided in the form of a subsequent report within 15 calendar days from the date of its receipt.

Requirements to submission of information on SUADR applied to the study product, including the study quadrivalent vaccine.

#### **Submission of other treatment safety reports:**

Within 15 calendar days from the date of receipt of the information, the sponsor has to provide regulatory authorities and LECs of trial sites with other safety information which can affect evaluation of the risk-benefit balance associated with the treatment performed or can require significant modifications of the treatment performed during the study or the study methods. This safety information may include:

- Clinically significant increase of the expected rate and a change in the nature of the expected serious adverse reactions.
- SUADRs that occur in a study subject after completing the participation in a clinical study.
- New data related to the clinical study that may affect the safety of volunteers, such as:
  - Study-related SEAs, on the basis of which changes are required to study protocol.
  - The lack of effectiveness of the study drug used in a life-threatening pathology.
  - New important safety data from recently completed animal studies (identified carcinogenic effects and effects similar in severity and importance).

Strictly confidential. Proprietary Information.  
[name]

- Premature study termination or suspension of the study in another country (countries) due to a change in the safety profile of a similar study drug.
- Other safety data that alter the benefit-risk profile for study subjects.
- Recommendations of the independent evaluation committee of the results of a clinical study regarding the safety profile of a study drug.

Apart from submission of urgent reports, the sponsor company has to submit an annual periodic report on safety of the study product to regulatory authorities during the whole period of the clinical trial.

Information on the periodic report on safety of the study product is submitted to LECs of trial sites in the form of a brief description of the report basic content with an organized list of serious adverse drug reactions attached.

### 7.3.5. Pregnancy

If a female volunteer becomes pregnant while participating in the study, administration of the study drug must be discontinued immediately.

Pregnancy as such is not an AE except in cases where there is a reason to believe that the use of the study drug led to a decrease in the efficacy of contraceptives. Congenital abnormalities and birth defects in children of study subjects are considered SAEs. Medical abortions, as well as any serious complications during pregnancy (including spontaneous abortions) should be recorded as SAEs. Planned abortions without complications are not considered AEs.

All cases of pregnancy observed during the study (including cases of pregnancy of sexual partners of volunteers participating in the study) should be appropriately recorded. If a pregnancy is confirmed, the investigator must notify the sponsor's authorized representative on pharmacovigilance in the form of a pregnancy report. Then, the sponsor shall be provided with the information about the pregnancy outcome. Pregnancy of a study participant and sexual partners of male volunteers is recorded from the moment of the first injection of the study drug and until the Visit of study completion.

The outcome of each pregnancy (spontaneous abortion, elective abortion, birth of a normal child or a child with congenital anomalies or birth defects) must be recorded, even if the female volunteer has terminated her participation in the study.

## 7.4. The method and duration of observation of subjects after the occurrence of adverse events

If AEs or their complications are not resolved, the investigator has to conduct a follow-up of study of subject's condition. Follow-up has to be conducted until resolution or stabilization of the AE and its consequences in a condition considered as appropriate by the investigator or until the identification of the cause of the AE not associated with the study product administration.

---

Strictly confidential. Proprietary Information.  
[name]

## 8. STATISTICAL ASPECTS OF CLINICAL STUDY

### 8.1. Description of statistical methods

Descriptive statistics will be provided for all demographic and other baseline characteristics, immunogenicity, efficacy, and safety, as well as for changes (if applicable) in the course of the study for the time points of assessment and for therapeutic groups (groups A, B, C, and pooled B and C group). Descriptive statistics for quantitative variables will include mean, standard deviation (SD), median, first and third quartiles, minimum and maximum, and the number of valid observations. Qualitative parameters will be shown as frequencies and shares in per cent. 95 % confidence intervals around point estimate are also provided (where applicable). Descriptive statistics for immunogenicity and immunological efficacy parameters will be provided for antigens.

#### *Efficacy analysis*

The following immunogenicity parameters will be presented with the respective two-sided 95 % confidence intervals for antigens and therapeutic groups:

Before and after immunization:

- Geometric mean antibody titers (GMAT).
- The share of subjects achieving seroconversion.

After immunization:

- The share of subjects achieving seroconversion.
- Coefficient of increase of mean geometric antibody titer versus baseline before immunization (GMAT ratio before and after immunization).

Efficacy parameters will be evaluated by available data, without restoration of missing data.

Testing of statistical hypotheses will be performed for Group A (Grippol® Quadri vaccine) as compared with:

- pooled data of groups B and C (Grippol® Plus) for antigens H1N1 and H3N2, separately for each antigen;
- data of group B for Yamagata lineage antigen;
- data of group C for Victoria lineage antigen.

#### *Primary variable*

For comparison, the primary change in the proportion of persons with seroconversion (the ratio of the number of volunteers in whom the antibody titer [at least 1:40] increased by more than 4 times compared with the baseline [method of determination — hemagglutination-inhibition reaction]) according to an assessment 21 days after vaccination (Visit 7, Day 22 ± 1) the statistical hypothesis will be tested that the study vaccine is “not worse than” the comparator vaccines with an established 15 % limit of “not worse”.

---

Strictly confidential. Proprietary Information.  
[name]

$H_0: \pi_1 - \pi_2 \geq 0.15$   $H_A: \pi_1 - \pi_2 < 0.15$ ,

$\pi_1$  и  $\pi_2$  – the share of subjects achieving seroconversion for the reference vaccine and the test vaccine respectively.

The numbers of subjects achieving seroconversion according to the evaluation at Day 21 after immunization are presented with the respective two-sided 95 % confidence intervals for each antigen, by therapeutic groups. Testing of the hypothesis will be performed by calculation of two-sided 95 % confidence interval for the difference of shares based on logistic regression with the vaccine as a fixed factor and the baseline antibody titer as a covariate. The clinical center, sex, and age will also be considered as potential factors of the model. The conclusion that the test vaccine is not inferior to the comparator for the primary endpoint, the percentage of subjects achieving seroconversion according to the assessment on Day 21 after immunization will be made if the upper limit of the calculated 95 % confidence interval does not exceed the established limit of 0.15 (15 %). The calculation of the exact two-sided 95 % confidence interval for the difference in proportions will be presented as a supporting analysis. In case of proven non-inferiority of the test vaccine versus the reference vaccines for Yamagata and Victoria lineages antigens, the same two-sided 95 % confidence interval will be used for testing of the hypothesis of predominant efficacy of the test vaccine for the primary endpoint, the share of subjects achieving seroconversion according to the evaluation on Day 21 after immunization. The conclusion on predominant efficacy of the test vaccine can be made if the upper limit of the calculated 95 % confidence interval does not exceed 0. Since a statistically significant conclusion when testing "non-inferiority" hypotheses should be obtained in relation to one primary variable, the adjustment of significance level due to the presence of one primary variable will not be performed. The successive transition from testing of the non-inferiority hypothesis to testing of the statistical advantage hypothesis does not require adjustment of the significance level as well.

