## SYNOPSIS

Study Title	A Multicenter, Double-Blind, Randomized, Comparative Study of Safety, Reactogenicity, Immunogenicity and Efficacy of Quadrivalent Inactivated Subunit Influenza Vaccine Grippol® Quadri (NPO Petrovax Pharm, LLC, Russia) and Trivalent Inactivated Polymer-Subunit Vaccine Grippol® Plus (NPO Petrovax Pharm, LLC, Russia) in Parallel Groups, in Volunteers of 18 to 60 Years Old.
Study Design	A multicenter, double-blind, randomized, comparative study in parallel groups.
Clinical study phase	Phase II-III
Number of investigation sites	The list of clinical centers participating in this clinical study (with addresses and telephone numbers of clinical centers, names and positions of investigators responsible for conducting the study) is presented in a separate document. Up to 6 study centers in the Russian Federation are to participate in the study.
Study Drug	
Name: Grippol® Quadri, a quadrivalent inactivated subunit influenza vaccine
 
Dosage form: suspension for intramuscular and subcutaneous injection.
 
Dosage: 0.5 ml (1 dose)
 
Active ingredients:
 

- type A (H1N1) influenza virus antigen 5 µg;

- type A (H3N2) influenza virus antigen 5 µg;

- type B (Yamagata lineage) influenza virus antigen 5 µg;

- type B (Victoria lineage) influenza virus antigen 5 µg;

- immunoadjuvant Polyoxidonium® (azoximer bromide) 500 µg.

 
Administration route: intramuscular or deep subcutaneous injection
 
Sponsor: NPO Petrovax Pharm, LLC
 
Manufacturer: NPO Petrovax Pharm, LLC

Comparators	
Name: Grippol® Plus, trivalent inactivated polymer-subunit influenza vaccine containing Yamagata lineage type B influenza virus antigen.
 
Dosage form: suspension for intramuscular and subcutaneous injection.
 
Dosage: 0.5 ml (1 dose)
 
Active ingredients:
 

- type A (H1N1) influenza virus antigen 5 µg;

- type A (H3N2) influenza virus antigen 5 µg;

- type B (Yamagata lineage) influenza virus antigen 5 µg;

- immunoadjuvant Polyoxidonium® (azoximer bromide) 500 µg.

 
Administration route: intramuscular or deep subcutaneous injection
 
Sponsor: NPO Petrovax Pharm, LLC

Strictly confidential. Proprietary Information.  

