	
The volunteers will be randomized into 3 groups (at a ratio of 1:1:1). A block randomization method is used. An interactive web-response system (IWRS) with technical support service will be used for randomization. Investigators will be trained on working with IWRS system, and IWRS user guide will be handed out to all of them.
 
An identification name (ID) and a password will be used to access the system. These identifiers will be given to the authorized staff member of the investigation site prior to study initiation. Upon the volunteer randomization, the investigator receives information through the IWRS system on volunteer assignment to one of the vaccination groups that will be given to the volunteer during the study.
 
Volunteer stratification (by gender and age) will be made in the IWRS system for uniform assignment to groups.

Inclusion criteria	

1. Signed and dated volunteer's informed consent for participation in the study.

2. Men and women from 18 to 60 years old.

3. Healthy volunteers without signs of acute or chronic disorders, without history of chronic respiratory, cardiovascular, nervous system disorders, hepatic or renal disorders.

4. Previously not immunized, or previous influenza immunization occurring <math>\geq</math> 12 months before this study.

5. Subjects without history of influenza within <math>\geq</math> 12 months before this study.

6. Consent of volunteers (men and women) to use adequate methods of contraception (cervical caps with spermicide, diaphragms with spermicide, condoms with spermicide, intrauterine devices, oral contraceptives) or full abstinence for the whole period of the study.

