**3.3.1. Randomization**

The immunization group was determined randomly. Randomization will be based on a computer-generated randomization algorithm (randomization list), where each volunteer will be assigned a randomization number. That number will define the immunization group (A, B, or C) according to the randomization plan. That number will be assigned to the study subject for the entire period of the study and will be documented in volunteer's CRF.

The volunteers will be randomized into 3 groups (at a ratio of 1:1:1). A block randomization method is used. An interactive web-response system (IWRS) with technical support service will be used for randomization.

---

Strictly confidential. Proprietary Information.  
[name]

Investigators will be trained on working with IWRS system, and IWRS user guide will be handed out to all of them.

An identification name (ID) and a password will be used to access the system. These identifiers will be given to the authorized staff member of the investigation site prior to study initiation. Upon the volunteer randomization, the investigator receives information through the IWRS system on volunteer assignment to one of the vaccination groups that will be given to the volunteer during the study.

Volunteer stratification will be performed in the IWRS system according to the age and gender.

In an emergency medical case, the investigator can obtain information about a vaccine received by a volunteer through the IWRS system. Information about storage and unblinding of randomization codes is provided in Section 3.8.

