### Justification of the "non-inferiority margin":

In placebo-controlled studies of inactivated influenza vaccines, the seroconversion parameter in placebo group for the study antigens amounts to 0–1 %. The placebo does not contain the respective antigens, so it demonstrates no immunogenic activity [1].

Taking into account the expected seroconversion level in reference groups > 60 % and the minimum limit for influenza vaccines > 40 % of subjects achieving seroconversion, established by the guidelines for harmonization of requirements to influenza vaccine of the Committee for Proprietary Medicinal Products (CPMP), the non-inferiority margin 15 % is significantly below the superiority of the comparator over the placebo, which is appropriate.

For testing of non-inferiority null hypothesis for Grippol® Quadri and Grippol® Plus vaccines, taking into account the following parameters:

Strictly confidential. Proprietary Information.  
[name]

- Power: 80 %
- One-sided significance level: 2.5 %
- Non-inferiority margin: 15 %
- Expected share of subjects achieving seroconversion in Grippol® Plus group: 60 %
- Expected actual difference for the parameter in groups: 1 %

1 % of the calculated sample size for non-inferiority hypothesis, primary dichotomized parameter and uniform assignment into groups (1:1) is based on the following formula [5,6]:

$$n = \frac{(z_\alpha + z_\beta)^2}{(\delta - \Delta)^2} [\pi_1(1 - \pi_1) + \pi_2(1 - \pi_2)]$$

where  $n$  — the number of patients in each group being compared;

$\pi_1$  — percentage of subjects achieving seroconversion in the reference vaccine group;

$\pi_2$  — percentage of subjects achieving seroconversion in the test vaccine group;

$\Delta = \pi_1 - \pi_2$  — the expected difference between percentages of subjects achieving seroconversion in the reference vaccine and test vaccine groups;

$Z$  — critical values of standardized normal distribution;

$\delta$  — non-inferiority margin.

according to the calculation as per the given formula using software package PASS 12, there shall be at least 193 volunteers in each therapeutic group (579 volunteers in total).

Thus, the minimum required sample size should be: 193 volunteers in each of the three groups (579 volunteers in total).

Taking into account the dropout during the study (5 %), the required number of volunteers has to be increased to 204 per group (612 in total).

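### The primary model should include the sex and age strata and be fixed before unblinding; at present sex, age and centre are optional terms with no inclusion rule

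*Combined protocol and SAP*

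**What the plan says.** **Randomisation.** Section 3.3.1 states: "Volunteer stratification will be performed in the IWRS system according to the age and gender". The Synopsis adds the purpose: "Volunteer stratification (by gender and age) will be made in the IWRS system for uniform assignment to groups". Neither place gives the age bands, and neither names centre as a stratum. The Synopsis also says: "Up to 6 study centers in the Russian Federation are to participate in the study".

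**Primary analysis.** In Section 8.1 (Primary variable) the confidence interval for the difference in seroconversion, reference minus test, is "based on logistic regression with the vaccine as a fixed factor and the baseline antibody titer as a covariate". These are the only committed terms. Then follows: "The clinical center, sex, and age will also be considered as potential factors of the model". Non-inferiority is concluded if the upper 95 % limit does not exceed 0.15. For Yamagata and Victoria the same interval is then used for superiority, against 0. There is one supporting analysis: "The calculation of the exact two-sided 95 % confidence interval for the difference in proportions will be presented as a supporting analysis".

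**Secondary analyses.** The sentence about centre, sex and age recurs for the GMAT ANCOVA and for the seroprotection model. Both of those use the log of the baseline titer; the primary model does not say log.

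**Rules that might close the gap.** Section 8.6 says only that statistical processing can start once the database is closed. Section 8.7 applies when a planned method cannot be used. Neither governs a choice that the plan itself leaves open.

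**The concern.** There are two separate problems.

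1. **The strata may be left out.** Stratified allocation removes chance imbalance between arms on sex and age. If those factors predict seroconversion, a model without them still counts their variation as noise, so the standard error is larger than the design warrants.
2. **The model is not fixed.** Three optional terms give 2 × 2 × 2 = 8 candidate primary models for each of four antigens. Further choices lie behind them: age banded or continuous, how centres are coded, baseline titer raw or logged, and whether all antigens share one model. Choosing among them after seeing the results would not even be a deviation from the plan.

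The trial's conclusion depends on which side of 0.15 a single limit falls, so even a small dependence on model choice touches the primary claim, and the superiority claim for the B lineages as well.

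**Working it through.** **1. The plan's own figure.** Inputs from Section 8.2: reference rate 0.60, expected difference 0.01 (so test rate 0.59), margin 0.15, one-sided level 2.5 %, power 80 %.

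n = (z_α + z_β)² [π₁(1 − π₁) + π₂(1 − π₂)] / (δ − Δ)²
= (1.960 + 0.842)² × (0.2400 + 0.2419) / 0.14² = 192.98, so 193 per group.

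With 5 % dropout, 193 / 0.95 = 203.2, so 204. Both figures match the plan. The formula contains no covariates, so the number does not depend on which covariates are used.

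**2. Cost of omitting the strata.** The documents give no covariate effects, so these are assumed. In 3,000 simulated trials of 193 v 193, with stratified blocks, log baseline titer in every model, odds ratios of 1.5 for sex and 0.6 for age, and a centre SD of 0.3:

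- mean SE without sex and age 0.0463; with them 0.0457. That is 1.4 % wider before rounding, equivalent to 193 × (1.014² − 1) ≈ 5 volunteers per group;
- effect on the upper limit: 1.96 × (0.0463 − 0.0457) ≈ 0.0012, or about 0.12 percentage points against a 15-point margin;
- with centre also added, SE 0.0452. The total gap is then 2.4 %, but the part due to centre is not a cost of ignoring the stratification.

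A rough check: two evenly split binary strata with log-odds effects b₁ and b₂ account for a share s ≈ p(1 − p)(b₁² + b₂²)/4 of the outcome variance, and omitting them inflates the SE by 1/√(1 − s). With p = 0.595, p(1 − p) = 0.241:

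- b = 0.4 and 0.4: s = 0.0193, inflation 1.0 %;
- odds ratios 1.5 and 0.6 (b = 0.405 and −0.511): s = 0.0256, inflation 1.3 %;
- b = 0.8 and 0.8: s = 0.0771, inflation about 4 %.

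So 1 to 1.5 % describes moderate effects. It would be larger only if sex and age were both strong predictors.

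**3. Error and power across models.** A second simulation used 193 v 193, allocation balanced within sex by two age bands, six centres, a baseline titer effect of −0.5 per SD, and a standardised risk difference with a delta-method interval. Log-odds effects of sex and age were 0.4 (moderate) or 0.8 (strong), with centre effects up to ±0.4 or ±0.8. There were 3,000 trials at a true 15-point deficit and 2,000 at the planned 1-point difference.

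| Model | Non-inferiority claimed at 15-point deficit, moderate / strong | Power at 1-point difference, moderate / strong |
|---|---|---|
| Vaccine + baseline titer | 2.1 % / 2.1 % | 83.3 % / 83.4 % |
| + sex and age | 2.2 % / 2.4 % | 84.0 % / 85.0 % |
| + sex, age and centre | 2.3 % / 2.6 % | 84.5 % / 86.7 % |
| Most favourable of eight | 2.7 % / 3.3 % | 86.2 % / 88.3 % |

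The eight models disagreed on the non-inferiority verdict in 0.9 to 1.9 % of trials at the margin and in 4.7 to 6.8 % at the planned difference. The simulation in step 2 gave 2.0 to 2.3 % for any fixed model and 2.6 % for the most favourable.

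**4. Simulation error.** With 3,000 trials the standard error of a 2.6 % rate is √(0.026 × 0.974 / 3000) = 0.29 points, a range of about 2.0 to 3.2 %. For 2.7 % the range is about 2.1 to 3.3 %. Both include 2.5 %. For 3.3 % it is about 2.7 to 3.9 %, which does not.

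**The case against.** The strongest reply is that little is at risk. Baseline titer is already fixed in the model. The supporting exact interval names no covariates, so a verdict that hinged on covariate choice would show up beside it. Planned power comes from an unadjusted formula and does not rely on these terms. Leaving the strata out makes a false non-inferiority claim, if anything, less likely. All of this stands and limits the size of the point. It does not supply a rule: the supporting interval is not the decision criterion, and nothing fixes the model that is.

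A reader might infer more than the documents support:

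- **That omitting the strata biases the result or invalidates the test.** It does not. The error rate was about 2.1 % without them and 2.2 to 2.4 % with them, a difference within simulation error.
- **That model choice is shown to inflate the error seriously.** Picking the best of eight must raise the error relative to any fixed model, but an excess over 2.5 % is clear only under the strong assumed effects.
- **That centre is a stratum being ignored.** Neither description of the randomisation names it. The case for settling it in advance is ordinary pre-specification in a multicentre trial.
- **That the sample size is wrong.** It reproduces exactly.

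The simulations also cover only the 193 v 193 comparisons, which are those for the B lineages. For H1N1 and H3N2 the plan pools groups B and C, so standard errors are smaller there and the equivalent of 5 volunteers per group does not apply.

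**Conclusion.** The point holds as a modest, worthwhile improvement. On the text it is firm: sex and age are strata, the primary model need not include them, and no rule or date fixes the choice. On size it is small: an interval about 1 to 1.5 % too wide under moderate effects, and a one-sided error of about 2.6 to 3.3 % if the most favourable model were always taken. Those sizes rest on assumed covariate effects, two age bands, assumed centre effects, log or standardised baseline titer, and a standardised risk difference, none of which the primary analysis text specifies. The main reason to act is the missing pre-specification; the narrower interval is a secondary gain.

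**What to change.** In Section 8.1, under the primary variable, the GMAT ANCOVA and the seroprotection model, replace the sentence on candidate factors with a fixed list:

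- vaccine, log baseline titer, sex, and age in the bands used by the IWRS, with the same terms for all four antigens;
- centre declared in or out. If it is in, state the coding and a rule for small centres;
- for the primary endpoint, the reference-minus-test risk difference and its 95 % interval obtained from that logistic model by standardising over the analysed volunteers, with the variance method named;
- the model finalised and dated before unblinding. If unblinding has already happened, say so and label the choice accordingly.

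The exact unadjusted interval can stay as the supporting analysis. The change needs no extra volunteers, visits or samples, and 193 (204 with dropout) per group stands. It does require the age bands to be taken from the IWRS specification, because the protocol does not give them, and a decision on centre.
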